9.4.7 Primary Efficacy Analysis

The primary efficacy endpoint is the percentage of subjects achieving an ACR20 response and remaining on randomized treatment and in the study at Week 12, analyzed using the ITT population as the primary efficacy analysis. Supportive analyses of the primary endpoint will also be done using the mITT, if sufficiently different from the ITT population, and PP populations.

The ACR20 response at Week 12 for each of the OKZ 64 mg treatment groups (q2w and q4w) will be compared with placebo using a 2×2 chi-squared test for equality of proportions.

The overall Type I error rate will be controlled using a procedure in the strong sense at a 1-sided $\alpha = 0.025$ for testing multiple hypotheses for the 2 OKZ treatment groups versus placebo across the primary and secondary endpoints as described in Section 9.4.6.

As a supportive analysis, the difference between proportions of responders in each of the OKZ treatment groups and placebo (relative risk) will be estimated together with the corresponding 97.5% 2-sided confidence interval for difference of proportions using the Newcombe hybrid score method.

Missing data and data collected post premature study treatment discontinuation will be handled as described in Section 9.4.9.1.

9.4.8 Analysis of Secondary and Other Efficacy Endpoints

Analysis of secondary and other efficacy endpoints defined in Sections 4.2 and 4.3 will be based on the ITT population. Supportive analyses of the secondary endpoints will also be done using the mITT, if sufficiently different from the ITT population, and the PP population.

Secondary and other efficacy endpoints that are binary in nature will be analyzed using the same methodology as the primary endpoint.

Secondary and other efficacy endpoints that are continuous in nature will be analyzed using an ANCOVA model adjusted for the baseline value of the corresponding parameter.

Multiplicity control procedure to be applied for hypothesis testing related to the secondary endpoints is described in Section 9.4.6.

Missing data and data collected post premature study treatment discontinuation will be handled as described in Section 9.4.9.1.

9.4.9 Handling of Missing Data and Data Following Premature Discontinuation of Randomized Treatment

9.4.9.1 Primary Analysis of Primary, Secondary, and Other Efficacy Endpoints

Data Following Premature Discontinuation of Randomized Treatment

In this study, subjects who discontinue randomized treatment prematurely will be required to remain on study and be evaluated as per the planned Schedule of Events. For the main analysis of all binary endpoints, inability to remain on randomized treatment through the time point of interest is defined as treatment failure (non-response). For the main analysis of continuous endpoints, subjects who discontinue randomized treatment prematurely but remain on study through the time point of interest will be included using all collected measurements, including those from assessments post treatment discontinuation.

Missing Data Resulting from Study Withdrawal

The main method for handling missing data resulting from premature withdrawal of a subject from the study will be based on a clinical approach where no treatment benefit will be attributed to study treatment at any time point post-study withdrawal, if the subject was unable to complete the study for the planned duration.

Therefore, for all binary endpoints, all subjects who discontinue prematurely, regardless of reason, will be considered as nonresponders with respect to the definition of the corresponding endpoint.

Similarly, for all endpoints that are continuous in nature, a return to baseline values will be assumed and will be implemented using a multiple imputation (MI) methodology allowing to account for the uncertainty of missing data according to the methodology of Rubin (Rubin, 1987). Imputed values will be sampled from a posterior Bayesian distribution of the baseline values of each continuous parameter (for all treatment groups combined) using a regression imputation model with age, sex, time from RA diagnosis to first study dose, and duration of prior MTX treatment as predictor variables. Multiply imputed data will be analyzed with an ANCOVA model and the results will be combined using the Rubin's rule (Rubin, 1987). Additional details will be provided in the SAP.

Intermediate Missing Data

Missing data may also result from missed intermediate visits for subjects who completed the study. For all binary endpoints, missing intermediate responder status will be imputed from the surrounding visits. If the status at visits both before and after the missed visit is classified as responder, the subject will be considered a responder at the missed visit. Otherwise, the subject will be considered a nonresponder. If an assessment for a given binary endpoint at the last visit is missing for a completing subject, data from the 2 previous visits will be used with the same logic for determining the response status. For the ACR20/50/70 endpoints, if only some components of the response criteria are missing but the available components allow classifying the subject as a responder, the responder category will be used. Otherwise, the method based on surrounding visits as described above will be applied. Similarly, for all continuous endpoints, an average of values from the surrounding visits will be imputed for the missing visit.

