4.2 Secondary Efficacy Endpoints

The following secondary efficacy endpoints will be evaluated:

- Percentage of subjects achieving low disease activity, defined as DAS28 (CRP) <3.2, and remaining on randomized treatment and in the study at Week 12
- Improvement of physical ability from baseline to Week 12, as measured by the Health Assessment Questionnaire-Disability Index (HAQ-DI)
- Percentage of subjects achieving an ACR50 response and remaining on randomized treatment and in the study at Week 24
- Percentage of subjects with Clinical Disease Activity Index (CDAI) ≤ 2.8 (remission) and remaining on randomized treatment and in the study at Week 24

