4.3 Other Efficacy Endpoints

The following additional efficacy endpoints will be used to compare OKZ with placebo:

- Proportion of subjects achieving an ACR20, ACR50, and ACR70 response and remaining on randomized treatment and in the study, assessed at all other applicable time points
- Proportion of subjects with Simplified Disease Activity Index (SDAI) ≤ 3.3 (remission) and remaining on randomized treatment and in the study, assessed at all applicable time points
- Proportion of subjects with CDAI ≤ 2.8 (remission) and remaining on randomized treatment and in the study, assessed at all other applicable time points.
- Proportion of subjects with DAS28 low disease activity (based on DAS28 [CRP] <3.2) and remaining on randomized treatment and in the study, assessed at all other applicable time points

- Proportion of subjects with improvement from baseline in HAQ-DI score ≥ 0.22 and remaining on randomized treatment and in the study, assessed at all applicable time points
- Change from baseline over time in DAS28 (CRP)
- Change from baseline to Weeks 12 and 24 in DAS28 erythrocyte sedimentation rate (ESR)
- Change from baseline to all other applicable time points in the measure of physical ability (HAQ-DI)
- Change from baseline to Weeks 12 and 24 in the scores for the following patient-reported outcome (PRO) measures:
 - Short Form-36 (SF-36) Physical Component Summary (PCS) and Mental Component Summary (MCS) total scores
 - European Quality of Life-5 Dimensions (EQ-5D)
 - Work Productivity Survey-Rheumatoid Arthritis (WPS-RA)
 - Functional Assessment of Chronic Illness Therapy – Fatigue Scale (FACIT-Fatigue)
- Change from baseline to all applicable time points in SDAI and CDAI
- Proportion of subjects with moderate to good responses for EULAR based on DAS28 (CRP) and remaining on randomized treatment and in the study, assessed at all applicable time points, where a moderate response is defined as either DAS28 (CRP) ≤ 5.1 with an improvement from baseline in DAS28 (CRP) > 0.6 and ≤ 1.2 , or DAS28 (CRP) > 3.2 with an improvement from baseline in DAS28 (CRP) > 1.2 , and a good response is defined as DAS28 (CRP) ≤ 3.2 with an improvement from baseline in DAS28 (CRP) > 1.2
- Change from baseline to all time points in the components of the ACR response criteria

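### Does the return-to-baseline imputation for continuous endpoints fail because it leaves out the subject's own baseline?

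*Combined protocol and SAP*

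**What the plan says.** Section 9.4.9.1 states a principle for subjects who withdraw from the study: "no treatment benefit will be attributed to study treatment at any time point post-study withdrawal". For continuous endpoints, "a return to baseline values will be assumed", and the mechanism is then given: "Imputed values will be sampled from a posterior Bayesian distribution of the baseline values of each continuous parameter (for all treatment groups combined"). The regression model uses "age, sex, time from RA diagnosis to first study dose, and duration of prior MTX treatment as predictor variables". Results are combined by Rubin's rules, and further detail is left to the SAP.

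The rule covers study withdrawal only. For stopping treatment, the same section says that "subjects who discontinue randomized treatment prematurely but remain on study through the time point of interest will be included using all collected measurements".

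The one continuous endpoint in the gated sequence is HAQ-DI, "Improvement of physical ability from baseline to Week 12" (Section 4.2). Under Section 9.4.8 it "will be analyzed using an ANCOVA model adjusted for the baseline value of the corresponding parameter".

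**The concern.** Return to baseline is commonly read as return to the subject's own starting value. Here baseline is the variable being modelled, so it cannot also be a predictor. Each draw is a plausible baseline for someone with the same four covariates, not the value that the subject actually had. The subject with a high baseline is imputed an improvement and the subject with a low baseline a worsening. Yet the endpoint is change from own baseline, the ANCOVA adjusts for own baseline, and the placebo-based sensitivity model in Section 9.4.9.2 conditions on it.

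At stake would be the HAQ-DI test at Week 12, second of the four secondary endpoints. Under Section 9.4.6, failure there stops testing of ACR50 and CDAI remission for that regimen. The supportive analysis in Section 9.4.9.2 that discards all data after treatment discontinuation uses the same imputation for more subjects.

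**Working it through.** **Inputs from the documents.** 140 per arm (9.1); one-sided 0.0125 per regimen (9.4.6); pooled baseline draw, four predictors, Rubin's rules (9.4.9.1); ANCOVA on baseline (9.4.8). About 10% are assumed to stop treatment before Week 12 (9.1). No study-withdrawal rate is given.

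**Assumed, because the documents give nothing.** HAQ-DI SD 0.6 (range 0.5–0.7); baseline to Week 12 correlation 0.6 (0.5–0.7); R² of the four predictors 0.10 (0.02–0.20); true difference −0.25; 4, 7 or 14 withdrawals per arm (3%, 5%, 10%); 20 imputations. The comparator centres each imputed value on own baseline and adds a residual with the variance seen in placebo completers.

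**The plan's own figures.** The stated power values, 100% for ACR20 and 98% for DAS28, reproduce as 99.9–100% and 98.4%. Both endpoints are binary with withdrawals counted as nonresponders, so this imputation does not touch them. No HAQ-DI figure is stated.

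**Step 1: one subject.** For a subject 1 SD above the mean at baseline, the expected imputed change is −(1 − R²) × SD = −0.90 × 0.6 = −0.54 (0.40 to 0.69 in size over the ranges). A subject 1 SD below gets +0.54. Own-baseline return gives 0. The endpoint "Proportion of subjects with improvement from baseline in HAQ-DI score" of at least 0.22 (4.3) is unaffected: it requires the subject to remain in the study, so no value imputed this way is compared with that threshold.

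**Step 2: the average.** If withdrawal is unrelated to baseline, both methods impute a mean change of zero in every arm, so the estimate shrinks by the withdrawn fraction. At 5%: 0.25 × 133/140 = 0.2375. Simulation (5,000 trials) agrees:

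| Withdrawal | Estimate, plan / own baseline | SE, plan / own baseline | SE ratio | Power, plan / own baseline |
|---|---|---|---|---|
| 3% | −0.2413 / −0.2413 | 0.0599 / 0.0590 | 1.015 | 97.1% / 97.1% |
| 5% | −0.2386 / −0.2383 | 0.0616 / 0.0601 | 1.025 | 95.8% / 96.6% |
| 10% | −0.2264 / −0.2264 | 0.0655 / 0.0626 | 1.046 | 91.6% / 93.5% |

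A repeat run gave power of 97.3% / 97.6% at 3% and 96.1% / 96.1% at 5%.

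**Step 3: withdrawal related to baseline.** Suppose withdrawn subjects in one arm start 0.5 SD (0.30) higher. The gap between methods is roughly w × (1 − R²) × shift. At 5% this is 0.05 × 0.90 × 0.30 = 0.0135; simulation gave 0.0124 (OKZ arm) and 0.0129 (placebo arm). At 3% it gave about 0.008. Against the standard error these are 0.008/0.060 = 0.13 and 0.013/0.062 = 0.21. At 10% the gap was 0.025. Over the input ranges it was 0.006–0.010, 0.010–0.016 and 0.017–0.031 at 3%, 5% and 10%.

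If all arms share the shift, the gap is proportional to the difference in withdrawal rates. With equal selection and 5% everywhere it was 0.2379 − 0.2372 = 0.0007. With rates of 4% and 7% and somewhat stronger selection it was about 0.01. Agreement therefore needs both equal rates and the same relation to baseline in each arm.

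**Step 4: which method is off?** With OKZ-only selection at 10%, the plan moves from −0.2264 to −0.2399 (0.0135) and the own-baseline version to −0.2146 (0.0118 the other way). Power is 94.7% for the plan and 90.4% for own baseline. With placebo-only selection it is 87.7% and 96.1%. The gap is a difference between two conventions, not an error in one.

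**Step 5: type I error.** Across the null cases the plan rejected 0.18% to 1.16% and the own-baseline version 0.26% to 1.40%, against 1.25% allowed (Monte Carlo error 0.16 points).

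**Step 6: cost of the alternative.** Residual SD is 0.6 × √(1 − 0.36) = 0.48, so imputed values have SD √(0.36 + 0.2304) = 0.77, 28% wider than baseline; the plan keeps 0.6. Dropping the residual lowers the SE at 5% from 0.0601 to 0.0572, a move of 0.0029. The plan differs from the own-baseline version by only 0.0616 − 0.0601 = 0.0015. The choice of residual matters more than the choice between methods.

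**The case for a change.** The best case for a change is that the plan will hold every subject's baseline and ignores it, that the section speaks of return to baseline without saying whose, and that a gated endpoint depends on the answer. With 10–15% withdrawal that is strongly unequal, or related to baseline in opposite directions by arm, the two methods differed by 0.05–0.06, about a fifth to a quarter of a 0.25 effect.

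Some of this stands. The individual-level mismatch is real, and so is the loss of precision: nearly 5% in the standard error at 10% imputed. But the section does say whose baseline: it names the pooled baseline values of all arms as the sampling distribution. The stress cases need withdrawal patterns for which the documents give no basis. The 10% in Section 9.1 is treatment discontinuation, and those subjects stay in the main HAQ-DI analysis with their observed data. The larger effect falls on the Section 9.4.9.2 supportive analysis, which is outside multiplicity control. Section 9.4.9.2 also already has a placebo-based imputation that conditions on own baseline, and a HAQ-DI responder analysis that counts withdrawals as failures.

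**Conclusion.** No change is needed. The plan states a population-level return to baseline with no treatment term, and this satisfies its principle of crediting no benefit after withdrawal. For the main HAQ-DI test at 3–5% study withdrawal unrelated to baseline, the cost against an own-baseline version is a standard error 1.5–2.5% larger and at most about one point of power. Type I error is not inflated in the cases run. If withdrawal rates or their relation to baseline differ between arms, the estimates differ by about 0.01 at these rates, in either direction. The own-baseline alternative is a fair choice, but it brings an arbitrary residual variance and a wider imputed distribution, and it loses power in some settings.

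All HAQ-DI inputs and study-withdrawal rates here are assumptions. The conclusion that the effect is small rests on study withdrawal being low and not grossly unequal, which the requirement to follow subjects after treatment discontinuation favours. A line in the SAP confirming the population-level reading would do no harm, but it would alter no analysis.

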4. SUMMARY OF STUDY ENDPOINTS

4.1 Primary Efficacy Endpoint

The primary efficacy endpoint is the ACR20 response at Week 12, where a responder is defined as any subject satisfying ACR20 criteria and remaining on randomized treatment and in the study at Week 12. This endpoint will serve to demonstrate that the efficacy of OKZ is superior to placebo.

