7. EFFICACY, SAFETY, PHARMACOKINETIC, AND HEALTH OUTCOME ASSESSMENTS

7.1 Efficacy Assessments

7.1.1 American College of Rheumatology 20%/50%/70% Response Criteria

ACR20/ACR50/ACR70 will not be calculated by the Investigator during the course of the study, but will be computed in the statistical database for analysis purposes.

The number of subjects who achieve an ACR20, ACR50, or ACR70 response at various time points will be calculated for OKZ and placebo. The calculations are based on a $\geq 20\%$, $\geq 50\%$, and $\geq 70\%$ improvement from baseline in the SJC assessed in 66 joints and in the TJC assessed in 68 joints; and a $\geq 20\%$, $\geq 50\%$, and $\geq 70\%$ improvement from baseline in at least 3 of the 5 remaining core set measures:

- Patient Global Assessment of Disease Activity (VAS).
- Patient Assessment of Pain (VAS).
- HAQ-DI.
- Physician Global Assessment (VAS).
- Level of acute phase reactant (CRP or ESR, using level of CRP in this study).

7.1.2 66-68 Joint Assessment

The 66-68 joint assessment evaluates 66 joints for swelling and 68 joints for tenderness and pain on motion. The hip joints can be assessed for tenderness, but not for swelling. The following joints are included:

- Temporomandibular, sternoclavicular, acromioclavicular, shoulders, elbows, wrists, interphalangeal (IP) on digit 1, distal interphalangeals on digits 2 to 5, proximal interphalangeals (PIP) on digits 2 to 5, metacarpophalangeal (MCP) on digits 1 to 5, hips (tenderness only), knees, ankles and tarsus; metatarsals, IP on toe 1, PIP on toes 2 to 5, and metatarsophalangeals (MTP) on toes 1 to 5.

As noted in Table 1 and Table 2, the joint assessor will be independent to the rest of the study team. An independent joint assessor, blinded to other study assessments as well as the dosing regimen, will be identified at each study site to perform the SJC and TJC. To ensure consistent joint evaluation throughout the study, individual subjects should be evaluated by the same joint assessor for all study visits, whenever possible.

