The method of handling missing data that considers discontinued subjects as nonresponders or imputes continuous data with baseline values may be regarded as not conservative if the proportion of subjects dropping out is greater in the placebo group than in the OKZ treatment groups. To address a possibility of this scenario, analysis of primary and secondary efficacy endpoints will be repeated using all collected data (including data post premature study treatment discontinuation) but with missing data after study withdrawal imputed under the following assumptions. Missing post-study withdrawal data for subjects discontinuing from the placebo group will be imputed under the assumption of the Missing-at-Random (MAR) mechanism, where these discontinued subjects are assumed to have post withdrawal values in line with similar placebo subjects who remained in the study, taking into account their values observed prior to discontinuation. For subjects discontinuing from the OKZ treatment groups, missing post withdrawal data will be imputed from the same MAR-based imputation model estimated from the placebo subjects, assuming that after discontinuation, the OKZ subjects will drift towards the mean response of the placebo group. This approach is likely to result in more favorable imputations for the placebo group compared with the nonresponder/return to baseline assumption, while for the OKZ treatment groups, it will not assume a treatment effect beyond the study effect and the effect of the background MTX therapy. This approach will be more conservative compared to the primary analysis if the proportion of subjects discontinuing from the study is greater in the placebo group than in the OKZ treatment groups.

This approach will be implemented with MI using 2 steps. First, intermediate missing data of each continuous parameter will be multiply imputed under the MAR assumption within each treatment group using a multivariate normal imputation model and the Markov chain Monte Carlo (MCMC) method. Second, intermediate missing data imputed in this way will then be used together with observed data for the estimation of the MAR-based model from the placebo group, which will be done using sequential regression imputation models applied to each continuous parameter (Ratitch et al, 2013). The MAR-based placebo imputation model for each parameter will be estimated based on data from placebo subjects and will

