include baseline value of the corresponding parameter and all post-baseline values prior to study discontinuation as explanatory variables. Post study discontinuation missing values in all 3 treatment groups will then be imputed from this single placebo imputation model.

Binary endpoints will then be computed from the multiply imputed data regardless of adherence to randomized treatment through the time point of interest based on the criteria of achieving the corresponding clinical response. Multiply imputed datasets will be analyzed using the same methods as in the primary analysis, followed by combining the results using Rubin's rule (Rubin, 1987).

Additionally, for the primary and secondary endpoints that are binary in nature, a tipping point analysis will be performed. First, binary response status at the time point of interest will be computed using all collected data regardless of adherence to randomized treatment through the time point of interest based on the criteria of achieving the corresponding clinical response. For subjects who withdraw from the study overall, all possible combinations of the number of responders and nonresponders in each treatment group will be considered. The results of analysis for all possible combinations will be summarized graphically, depicting a boundary between combinations that result in a statistically significant treatment effect vs not statistically significant. Clinical plausibility of the combinations on the boundary will be discussed in the Clinical Study Report to evaluate robustness of study conclusions to missing data.

For the secondary endpoint that measures physical ability based on the HAQ-DI improvement at Week 12, a continuous responder analysis will also be performed. Subjects will be considered responders at a specified improvement threshold if they experience percent improvement in the HAQ-DI score from baseline to Week 12 that is greater or equal to the specified threshold and if they remain on the randomized treatment and in the study through Week 12. This analysis will be performed for a range of improvement thresholds from 0 to 100% in 5% increments. The results will be summarized using a graph of proportion of responders in each treatment group versus improvement thresholds.

Sensitivity to Data Following Initiation of Rescue Medication

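### The partial-missing rule for ACR20/50/70 has no branch for proven non-response, so a subject whose observed components already rule out response can be counted as a responder

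*Combined protocol and SAP*

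**What the plan says.** Section 9.4.9.1 (Intermediate Missing Data) covers subjects who complete the study but miss an assessment.

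- **Surrounding-visits method, all binary endpoints.** "If the status at visits both before and after the missed visit is classified as responder", the missed visit counts as response; in any other case it counts as non-response. At the last visit, "data from the 2 previous visits will be used with the same logic for determining the response status".
- **ACR20/50/70 with only some components missing.** If "the available components allow classifying the subject as a responder, the responder category will be used". The next sentence disposes of the rest: "Otherwise, the method based on surrounding visits as described above will be applied".

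Two definitions bear on this. Section 4.1 says that "a responder is defined as any subject satisfying ACR20 criteria and remaining on randomized treatment and in the study at Week 12". Section 7.1.1 requires the threshold improvement in both the 66-joint swollen count and the 68-joint tender count, and "improvement from baseline in at least 3 of the 5 remaining core set measures".

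Sections 9.4.7 and 9.4.8 refer to Section 9.4.9.1 for missing data, so the rule governs the primary endpoint (ACR20 at Week 12) and the gated secondary endpoint ACR50 at Week 24.

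**The concern.** The rule treats the two kinds of conclusive partial data differently. Components that prove response are used. Components that prove non-response are set aside, and the status is borrowed from other visits. A subject who demonstrably failed ACR20 at Week 12 then becomes a Week 12 responder if the visits on either side were responder visits.

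The text does not name those visits. By Table 1, the nearest visits with every ACR component are Weeks 8 and 18 for Week 12, and Weeks 18 and 12 for Week 24; Week 14 has joint counts only. Week 18 falls after rescue medication may start (Section 6.13.3), and Section 9.4 keeps post-rescue data in all main analyses. An observed Week 12 failure could therefore be overturned partly by a response recorded under rescue. The rescue sensitivity analysis covers only Weeks 16 to 24.

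At stake is the classification behind the primary test. The error runs one way within an arm, since it can only add responders. Which arm gains more is not fixed by the documents.

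**Working it through.** **1. The plan's own figures.** Inputs from Sections 9.1 and 9.4.6: 140 per arm; ACR20 of 25%, 50% and 55% (placebo, q4w, q2w); DAS28 (CRP) <3.2 of 10%, 22% and 30%; 1-sided alpha 0.0125 per regimen; gating within regimen. A simulation of 400,000 trials gives disjunctive power of 99.97% for ACR20 (stated 100%) and 98.5% for DAS28 (stated 98%). Both are reproduced, and nothing below disputes them.

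**2. What partial data can prove.** Each of the 7 components is improved, not improved or missing. Partly missing patterns number 3^7 - 2^7 - 1 = 2,187 - 128 - 1 = 2,058. Applying Section 7.1.1:

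| Patterns | Total | Prove response | Prove non-response | Undetermined |
|---|---|---|---|---|
| All partly missing | 2,058 | 35 | 1,307 | 716 |
| One component missing | 448 | 25 | 361 | 62 |
| Only CRP missing | 64 | 5 | 53 | 6 |

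The CRP row can be checked by hand. A joint count fails in 48 of the 64 patterns. In the other 16, the four remaining measures show at least 3 failures in 5 patterns, at least 3 successes in 5, and a 2-2 split in 6. So 48 + 5 = 53 patterns prove non-response. These are pattern counts, not probabilities.

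**3. The rule applied literally.** Crossing component status (3) with status at the visit before (2) and after (2) gives 12 outcomes. Adding a proven-non-response branch changes exactly one: proven nonresponder with responder status on both sides goes from responder to nonresponder.

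*Example.* At Week 12 the tender joint count improves by less than 20% and CRP is missing, so ACR20 is impossible. If Weeks 8 and 18 are responder visits, the written rule makes the subject a Week 12 responder.

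**4. Size.** Expected false responders per arm = 140 x m x s x f, where m is the partial-missing rate, s the share of those cases with proven non-response, and f the probability that both neighbouring visits respond given proven non-response. None of the three is in the documents.

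- Assumed m: 2% to 5%, i.e. 2.8 to 7 subjects per arm.
- s and f come from an illustrative simulation: seven latent normal components at Weeks 8, 12 and 18; within-visit correlation 0.3 to 0.7; between-visit correlation 0.3 to 0.9; thresholds calibrated to the planned ACR20 rates; one non-joint component deleted at Week 12; 150,000 subjects per setting.

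| Arm | s | f | False responders |
|---|---|---|---|
| Placebo | 0.72-0.74 | 0.032-0.066 | 0.07-0.34 |
| q4w | 0.47-0.49 | 0.071-0.208 | 0.10-0.69 |
| q2w | 0.43-0.44 | 0.081-0.245 | 0.10-0.73 |

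For example, the placebo maximum is 7 x 0.74 x 0.066 = 0.34. Products of the rounded inputs can differ from the table in the second decimal. Compared within the same setting, the net shift in the ACR20 difference is +0.02 to +0.29 percentage points.

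*Equal flip rates in all arms* (f = 0.05 to 0.20; s = 0.73, 0.48, 0.43). Placebo gains 2.8 x 0.73 x 0.05 = 0.10 to 7 x 0.73 x 0.20 = 1.02 subjects. The olokizumab arms gain 2.8 x 0.43 x 0.05 = 0.06 to 7 x 0.48 x 0.20 = 0.67. The largest shift is q2w: (0.60 - 1.02)/140 = -0.30 points. The range is -0.03 to -0.30.

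**5. Effect on power.** For q4w, power = Phi[(d - 2.241 x SE0)/SE1], with SE0 the pooled and SE1 the unpooled standard error. At 50% vs 25%, SE0 = 0.0579 and SE1 = 0.0559, so (0.25 - 0.1297)/0.0559 = 2.15 and power is 98.4%. Moving d by about 0.3 points either way gives 98.2% to 98.6%.

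**6. A close result.** One subject moves an arm's rate by 1/140 = 0.71 points. Against 35/140 on placebo, 52/140 gives 1-sided p = 0.0141 (not significant at 0.0125) and 53/140 gives p = 0.0102 (significant).

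**The case against.** **The gap closes on a sensible reading.** The surrounding-visits method is there to impute a missing responder status. If a joint count has failed, the status is known and nothing needs imputing; Sections 4.1 and 7.1.1 support this. A careful programmer might well code it so. But the sentence on partly missing components is the specific one. It names a single conclusive case and sends all others to the surrounding visits.

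**The literal reading is selective.** Taken strictly, the visits next to Week 12 are Weeks 10 and 14, and those before Week 24 are Weeks 22 and 20. None has a full ACR assessment, so no false responder could arise. It is true that the visits are unnamed. On that reading, though, the method could never return a responder at Week 12 or Week 24, so the nearest assessable visits are the only workable meaning.

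**Details are deferred to the SAP.** Section 9.4 says so, and the document reviewed contains no separate SAP text. A repair there can be neither ruled out nor assumed.

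**A sensitivity analysis already handles it.** In Section 9.4.9.2, "intermediate missing data of each continuous parameter will be multiply imputed under the MAR assumption within each treatment group", and "Binary endpoints will then be computed from the multiply imputed data", so an observed failure stays a failure. That analysis also changes the handling of discontinuation and withdrawal, so it neither isolates this error nor corrects the primary classification. The tipping-point analysis varies only subjects who withdraw.

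**The effect is negligible and the same rule applies to every arm.** This stands. The size calculation even overstates it slightly by using all 140 subjects: with about 10% off treatment by Week 12 (140 x 0.9 = 126 per arm) the largest positive shift falls to about 0.25 points. No inflation of the Type I error rate was shown, and no size was computed for ACR50 at Week 24.

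**Conclusion.** The rule is wrong as written: it can assign responder status to a subject whose observed Week 12 data exclude it, against the endpoint definition. This is a stated rule that misclassifies, not merely a missing detail.

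It is a minor point. Only study completers still on randomized treatment, with conclusive partial data and responder status at both neighbouring visits, are affected. The shift lies between -0.30 and +0.29 points against planned differences of 25 and 30, and the stated powers of 100% and 98% are unaffected. The size rests on an assumed 2% to 5% partial missingness and assumed correlations or flip rates, and its sign depends on them. The logical gap depends on none of these, only on taking the nearest visits with full ACR data as the surrounding visits.

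**What to change.** Replace the two-branch rule in Section 9.4.9.1, and carry the same text into the SAP before unblinding:

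> If the components that were observed are enough to classify the subject as a responder or as a nonresponder, that status is used. The surrounding-visits method applies only when the observed components leave the status undetermined.

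It would help to name the surrounding visits for Weeks 12 and 24 in the same edit.

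The cost is one sentence in the protocol and the SAP. It needs no new data and leaves sample size and power unchanged.
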